## 6.1.2 Secondary study parameters/endpoints (if applicable)

Secondary outcomes are:

- Recurrence at 5 year (identified by record linking[BE] or general practitioner data[NL])
- Recurrences needing surgery
- Recurrence risks stratified by patients and surgical characteristics (Sex, age)
- Recurrence risk in the operative subgroup stratified for laparoscopic vs open surgery
- Morbidity from elective adhesiolysis:
  - Serious adverse events and complications, graded by Clavien-Dindo score.
  - Intra-operative events (i.e. bowel injury), graded by ClassIntra®

- ICU admission
- Reinterventions within 90 days

Patient questionnaires at 1 and 2 years of follow-up

- Health-related quality of life measured by EQ5D
- Gastro-intestinal related quality of life measured by GIQLI
- Characteristics of abdominal pain
- Costs from healthcare perspective (measured by modified iMCQ)
- Costs from societal perspective (measured by modified iMCQ and iPCQ)
- Cost-effectiveness (incremental cost-effectiveness ratio, i.e. cost per QALY) Surgical follow-up
- History taking with focus on potential recurrences
  - Review of data from readmission in same hospital
  - Ask patients if there have been readmission to other hospitals
- Assessment of complaints related to obstruction
  - Chronic or recurrent nausea, bloating, abdominal pain
  - Unintended weight loss
- Physical examination focused on abdominal pain and incisional hernia

The full iMCQ and iPCQ questionnaires are quite extensive and elaborate for patients to fill out. Therefore a modified version of these questionnaires is applied, in which only the domains that are potentially affected by ASBO are included, as decided upon during an expert meeting with healthcare professionals and patient representatives. This method is frequently applied in cost-effectiveness research and also increases the number of patients completing the questionnaire.

## 6.1.3 Other study parameters (if applicable)

At baseline we will collect data on surgical history, co-morbidity, BMI, and substance use. During the surgery we will collect data on surgical approach, intraoperative events graded by Class-Intra, extent and location of adhesions (measured by Peritoneal Adhesion Index), Completeness of adhesiolysis, and use of barrier.

At the follow-up visits we will perform history taking and physical examination focused on identification of potential readmissions for ASBO at other hospitals, chronic complaints, and late surgical complications such as incisional hernia.

## 6.2 Randomisation, blinding and treatment allocation

Upon inclusion, patients will be randomized 1:1 to intervention or control. The randomization will be stratified for first episode of aSBO vs. recurrent episode of aSBO, and for the operative center. Patient with previous recurrences of aSBO have

an higher risk for recurrences as compared to patients presenting with a first episode. We also plan to perform subgroup analyses for patients presenting with a first or recurrent episode of aSBO. Adhesiolysis is a procedure that is difficult to fully standardize, because the approach and technique can vary based upon location and density of adhesions. Randomization is therefore stratified per center to correct for small differences in decision making regarding surgical techniques and approach. The number of included patients per stratum can be relative small, therefore random permuted blocks with a size of 4 or 6 will be used to ensure balanced randomization between the groups.

This is an open label trial. The marked differences between the intervention and control group do not allow for blinding of subjects, surgeons, and researchers.

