#### 4.3 Exclusion criteria

A potential subject who meets any of the following criteria will be excluded from participation in this study:

- Patient who are unfit for operation for surgical, anesthesiological or medical reasons as determined by multidisciplinary team assessment or pre-operative screening
- Patients with active malignancy, reducing life expectancy
- Patient who has undergone surgery for previous episodes of aSBO in the past six months.
- Patient who has undergone previous complete adhesiolysis with use of adhesion barriers.
- Pregnancy

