#### 6.3 Study procedures

Patients who recovered from aSBO by conservative treatment who meet the above inclusion and exclusion criteria are eligible for inclusion. Potential candidates are identified by treating surgeons and physicians at participating operative and referral centres. The treating surgeon or physician will discuss the option of participating in the study and give a short introduction on what participation entails at discharge. Furthermore, the physician will verbally ask permission to the patient for the study team to contact the patient and schedule an outpatient visit to an operative centre to provide full information on the trial and discuss participation, non-committal. Patients referred to discuss participation in the trial will receive written information about the trial at a minimum of 5 days prior to the outpatient clinic meeting. The outpatient clinic meeting will be scheduled within two weeks from discharge when the patient has fully recovered. At the outpatient clinic history taking and physical examination will be performed by a qualified surgeon and anaesthesiologist to confirm eligibility of the patient to participate. Further, detailed information about the intervention will be provided.

Patients who agree to participate in the study will provide written informed consent to be randomized.

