#### Multidisciplinary team meeting

Patients who are surgical, medical, or anaesthesiological unfit for surgery are to be excluded from the study. There is not a single pragmatic test to assess is a patient is fit for surgery. Therefore a weekly disciplinary team meeting with the experts centres will be conveyed, where cases in which there is doubt about the fitness of patient to undergo elective adhesiolysis can be discussed.

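### Section 6.2 prints the block sizes (4 or 6) for an open-label trial stratified by operative centre, without tying release of the allocation to a final fitness decision; both can be mended at almost no cost

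*Protocol*

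**What the plan says.** Section 6.2 fixes the allocation method. On ratio: "patients will be randomized 1:1 to intervention or control". On strata: "The randomization will be stratified for first episode of aSBO vs. recurrent episode of aSBO, and for the operative center". On blocks, because strata may be small: "therefore random permuted blocks with a size of 4 or 6 will be used to ensure balanced randomization between the groups". On masking, it says that the differences between the arms "do not allow for blinding of subjects, surgeons, and researchers".

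Eligibility turns partly on judgement. Section 4.3 excludes: "Patient who are unfit for operation for surgical, anesthesiological or medical reasons as determined by multidisciplinary team assessment or pre-operative screening". Section 6.3 says that at the operative centre's clinic "history taking and physical examination will be performed by a qualified surgeon and anaesthesiologist to confirm eligibility of the patient to participate". Its paragraph on the multidisciplinary team meeting concedes that no single test settles fitness and provides that, for doubtful cases, "a weekly disciplinary team meeting with the experts centres will be conveyed". Section 9.2 schedules the operation at the centre where the patient attended the clinic.

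Table 1 (Overview of Study Procedures, section 6.3) places randomisation at most 4 days after visit 1 and marks eligibility assessment at both steps. The protocol describes no central allocation system, no concealment procedure and no withholding of block sizes from sites.

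**The concern.** Permuted blocks return each stratum to balance every few patients. In an open-label trial stratified by centre, staff at an operative centre can count who was operated on and who was not in each of their two strata, and so can often tell which arm is likely next. The people able to keep that count also apply a discretionary fitness criterion. If the next arm can be guessed while fitness is still open, a patient could be deferred, sent to the team meeting or excluded partly according to the expected arm.

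Selection before randomisation is not repaired by intention-to-treat analysis. Section 8.1 adjusts only for episode type and hospital, so an imbalance in any other prognostic factor would stay in the primary comparison. Printing the block sizes adds to this: an observer who knows them can turn some likely guesses into certain ones.

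**Working it through.** **Inputs.** From section 6.2: 1:1 ratio, block sizes 4 and 6, strata formed by operative centre and first or recurrent episode. From section 4.4: 380 patients. Assumptions: the two sizes are equally likely, and strata hold 8 to 38 patients. With two strata per centre the average is 380/(2 × centres): 5 centres give 38, 10 give 19, 20 give 9.5; an average of 8 needs about 48 strata (380/8), or 24 centres. The protocol states no guess rate, so there is no figure of its own to reproduce.

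**Guess rate within complete blocks.** The rule is to name the arm that is behind and toss a coin when the arms are level. In a block of 2n the expected number of correct guesses is n + ½[4ⁿ/C(2n,n) − 1].
- Block of 4: 2 + ½(16/6 − 1) = 2.833, or 2.833/4 = 70.8%.
- Block of 6: 3 + ½(64/20 − 1) = 4.1, or 4.1/6 = 68.3%.
- Equal mix: (2.833 + 4.1)/10 = 69.3%.

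**Guess rate in finite strata (simulation).** 8 patients: 66.8%; 12: 68%; 19: 68%; 38: 69%. The arms are unequal before about 60% of allocations, and the guess is then right about 78-81% of the time. The rule needs only the running count, and the optimal guess with known sizes does no better (66.9% to 68.9%). Mixing 4 and 6 therefore does not defeat it. Adding blocks of 8 gives 66-68%.

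**Certain allocations.** Here knowledge of the sizes matters. With 4 and 6 mixed at random, an observer who knows the sizes and tracks the sequence can be certain of about 6% of allocations. Without the sizes, the comparable share is about 1%: the allocations made at an imbalance of 3, where these blocks always force the lagging arm.

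**Timing.** A doubtful case referred to the team at visit 1 could wait up to 7 days for a weekly meeting, whereas randomisation falls due within 4. The protocol does not say whether such cases must be settled before visit 1, or whether allocation waits for the verdict.

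**Cost of the stronger alternative.** Take a big-stick procedure: a fair coin unless the stratum imbalance has reached 4, then the lagging arm. Sections 8 and 8.1 account for centre and episode in the primary Cox model, so balance matters within strata. A stratum of n patients with final arm difference D keeps 4n₁n₀/n² = 1 − (D/n)² of its information, so the loss is the mean of (D/n)².

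| Patients per stratum | Loss, blocks of 4 or 6 | Loss, big stick (limit 4) |
|---|---|---|
| 8 | 1.8% | about 9% |
| 12 | 0.7% | 4% |
| 19 | 0.3% | 1.4% |
| 38 | 0.06% | 0.4% |

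The big stick brings correct guesses down to about 52-55%, but 4-11% of allocations are then forced.

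**The case against.** Randomly varied small blocks stratified by centre are conventional, and section 6.2 gives a reason for them: strata may be small. There are safeguards too. Referral-centre physicians, who also identify candidates, cannot follow the running balance. A surgeon and an anaesthesiologist both confirm eligibility, and doubtful cases can go to the expert centres. The text of sections 6.2 and 6.3 implies the usual order of eligibility, consent, then randomisation, and a second eligibility mark in Table 1 may be no more than a final check. All of this stands. It means the protocol shows an opportunity and an unstated safeguard, not a broken procedure.

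A reader might go further and infer an inflated type I error. If patients enrolled when surgery is expected had a 2-year risk d points lower than those enrolled when control is expected, the spurious arm difference would be (2g − 1)d. With g = 0.68 that is 1.8 points for d = 5 and 3.6 points for d = 10; at a 20% risk and no true effect, type I error would be about 7% and 14%. The documents give no basis for d or its sign. The one risk factor that section 6.2 names, episode type, is already stratified and modelled, and adhesion extent is recorded only during surgery (section 6.1.3). These figures are illustrations, not a forecast.

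A reader might also infer that replacing the blocks is practically free, because the overall arm imbalance stays small: an SD of 13.8 gives (13.8/380)² = 0.13%. That counts the wrong imbalance for a model that accounts for centre and episode.

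**Conclusion.** The point holds as a modest one. Allocations in this open-label, centre-stratified design can be guessed about two times in three (67-69% for 8-38 patients per stratum), and printing the block sizes raises the certain ones from about 1% to about 6%. The protocol neither withholds the sizes nor says that fitness is settled before an allocation is released, and the 4-day limit and weekly meeting leave room for an open verdict. Whether anyone would act on this, and in which direction the result would move, is unknown.

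The figures assume equally likely block sizes, an unstated number of centres, and operative-centre staff who keep count by stratum. The guess rate changes little across the range of stratum sizes. The evidence supports closing the gap in disclosure and timing. It does not show that the blocks must be replaced.

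**What to change.** 1. Remove the block sizes from the site-facing protocol and hold them in a restricted randomisation document. Because 4 and 6 are already disclosed, change the set, for example by adding further sizes.
2. State in section 6.2 that allocation is concealed, by what system, and that it is released only after consent and the final fitness decision, including any team-meeting verdict, are recorded.
3. Reconcile the 4-day limit in Table 1 with the weekly meeting so that no fitness decision is open at allocation. Section 9.2, which allows consent at a digital visit 4-5 days after the clinic, should be read against the same limit.

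The cost is a short amendment and a change to the randomisation set-up, with no extra patients. The gain is limited: most certain allocations and late exclusions go, but the overall guess rate falls only slightly (66-68% with blocks of 8 added).

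Optional: a big-stick procedure with limit 4 would bring guesses down to about 52-55%. It is reasonable if strata turn out large and hard to justify if they are small, given losses of 0.4% to about 9% against 0.06% to 1.8% now. The trial statistician should decide once the number of centres is known.

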#### 6.3 Study procedures

Patients who recovered from aSBO by conservative treatment who meet the above inclusion and exclusion criteria are eligible for inclusion. Potential candidates are identified by treating surgeons and physicians at participating operative and referral centres. The treating surgeon or physician will discuss the option of participating in the study and give a short introduction on what participation entails at discharge. Furthermore, the physician will verbally ask permission to the patient for the study team to contact the patient and schedule an outpatient visit to an operative centre to provide full information on the trial and discuss participation, non-committal. Patients referred to discuss participation in the trial will receive written information about the trial at a minimum of 5 days prior to the outpatient clinic meeting. The outpatient clinic meeting will be scheduled within two weeks from discharge when the patient has fully recovered. At the outpatient clinic history taking and physical examination will be performed by a qualified surgeon and anaesthesiologist to confirm eligibility of the patient to participate. Further, detailed information about the intervention will be provided.

Patients who agree to participate in the study will provide written informed consent to be randomized.

#### Multidisciplinary team meeting

Patients who are surgical, medical, or anaesthesiological unfit for surgery are to be excluded from the study. There is not a single pragmatic test to assess is a patient is fit for surgery. Therefore a weekly disciplinary team meeting with the experts centres will be conveyed, where cases in which there is doubt about the fitness of patient to undergo elective adhesiolysis can be discussed.

## Cross-over of patients

Patients randomized to the control arm of the trail are offered the possibility to crossover to the intervention group in case they have developed a recurrent episode of
ASBO during the study period. A recurrent episode of ASBO is defined as a new
episode of acute bowel obstruction during the follow-up after randomization,
causing symptoms of bloating, nausea and abdominal pain, and requiring hospital
admission, and no other cause for obstruction on CT (as defined in the inclusion
criteria under 4.1). Following such recurrent episode, patients in the control arm can
decide for cross-over in shared decision making with their treating surgeon and not
randomized. Data until the first episode of recurrence will be analyzed according to
intention to treat.

## Surgery

Patient randomized to the intervention will undergo surgery within 6 weeks following inclusion. Surgery will be performed in accordance to the description of the intervention in chapter 5 of the protocol. Peri-operative care will be performed according to local protocols for elective laparoscopic surgery in the operative centres. Based on previous experiences we expected adhesiolysis to be performed laparoscopically in 70-80% of patients. Average hospital stay following laparoscopic adhesiolysis is 2 days. In converted and open surgery cases, the average stay is 5 days. Operatively treated patients will have a single outpatient visit to evaluate the recovery at 6 weeks post- surgery, or more frequent if a complication has occurred (as appropriate in the care for that complication). No specific follow-up is performed after this single post-operative outpatient visit.

#### Control arm

For patients randomizing to the control arm no specific follow-up care is performed as per usual care.

#### Recurrence

Patients will present at their local hospital (referral of operative centre) in case of symptoms of recurrence of bowel obstruction, including lower abdominal pain, bloating, nausea, and vomiting. Although most cases of bowel obstruction are caused by adhesions, especially after previous episodes of aSBO, there are a few other aetiologies of bowel obstruction such as strangulated abdominal wall hernia or tumours. To confirm the adhesive aetiology of small bowel obstruction a CT-scan will be made. CT-scan is known to be more than 90% accurate in distinguishing adhesions from alternative causes of bowel obstruction.(2) A readmission for obstructive symptom with CT or operative confirmation of adhesive aetiology will be scored as recurrence under the primary outcome.

#### Data collection

Follow-up questionnaires will be sent at 6, 12 and 24 months of follow-up. The questionnaire will include surveys of health-related quality of life (EQ5D), abdominal complaints, healthcare costs (iMCQ) and productivity (iPCQ). In addition the questionnaire will cover potential missed episodes of recurrence (e.g. readmission for recurrence when travelling abroad). In case a potential missed episode of recurrence is identified, additional medical information of the readmission is requested to verify if this was an episode of recurrence.

Table 1 provides an overview of the study procedures and moment for data capture. Long-term follow-up

We will perform an extended follow-up of 5 years for the primary outcome of readmission based on data from participating centers and general practitioner data. General practitioner data are important sources for the long-term follow-up as patients
might present at a different hospital with a recurrence of ASBO. In both the Netherlands and Belgium correspondence from all hospital admissions is held by the general practitioner. After review of data from participating hospitals, short questionnaires will be sent to general practitioners to identify potential readmissions for
ASBO outside the group of participating hospitals. We have experience with these
questionnaires in previous studies, and this methods has been shown to accurately
identify readmissions for ASBO. Additional hospital data is requested to verify diagnosis of ASBO in case a potential episode of recurrence is detected through general
practitioner data. Participants will be asked for oral and written consent at inclusion
to contact their general practitioner and other hospitals in the future for long-term follow-up.

In Belgium, general practitioner care is not fully centralized. In case it is difficult to obtain the required information from general practitioners, we will use record linkage to identify potential relevant readmissions using the following procedures by KCE.

After the completion of the study the Sponsor will transfer the pseudonymised study data set to KCE. KCE will request approval from the competent chamber of the Information Security Committee (ISC) to have the relevant study data linked with e.g. IMA data by a trusted third party (TTP, eHealth platform) using the participant national number.

The participant information and consent include wording that the national number will be recorded on site by the investigator for later data linkage, but will not be included in trial database available to the sponsor or any other third party. The participant information and consent will also include that in case the participant is randomized, it is planned that a trusted third party (TTP, eHealth platform) will receive and use the national number to link with IMA administrative data. To this end, KCE will receive the link between the study number and the national number under pseudonymised form. KCE will never be able to use the link without authorisation of the ISC and the intervention of the TTP. This data linkage is planned to obtain a more

complete data set containing costs related to health care paid by the compulsory health insurance and the participant that will be used for the analysis of effectiveness and cost-effectiveness of the intervention by KCE. The processing of personal data for this analysis is necessary for the performance of a task carried out in the public interest, as specified in the law defining KCE's missions and tasks. To the extent the personal data is related to health, the processing is necessary for scientific or statistic purposes, as specified in the law defining KCE's missions and tasks. For all processing related to the analysis of effectiveness and cost-effectiveness of the intervention, KCE is the controller.

KCE and Sponsor have entered into a research agreement detailing the roles and responsibilities of each party, as well as other legal aspects of this collaboration, including the right to use and access of KCE to the Study Data.

Background" means any intellectual property (IP), data, materials, information owned or controlled by the Sponsor or a Site and required to run this Study. Sponsor will identify such Background including the legal restrictions of which Sponsor, or Sites are aware that may affect the use of the Background for the purpose of the Study or the rights granted to KCE under this Agreement.

The Study Data consist of this protocol, including amendments, the electronic forms for data capture, including the annotations and guidance for use, the electronic data-base of the pseudonymized clinical and non-clinical data collected using data capture, including the log of changes from data entry to database lock, study reports based on these pseudonymized data, and any data or reports generated at a later stage, e.g. based on exploratory analyses or stored samples.

"Foreground" means any Study Data, and any tangible biological, chemical and physical material and inventions, that are generated, acquired, discovered, conceived, developed, created, exemplified or derived as a result of carrying out the Clinical Study, whatever its form or nature, whether it can be protected or not, as well as any Foreground IP. Sponsor acknowledges that the main purpose of the research performed under this Agreement is to generate results that will serve the general public interests, and specifically the interests of the patients and public

healthcare decision making bodies, and, therefore, undertakes not to exploit the Foreground in any way that is or could be detrimental to such interests.

The Sponsor owns the Study Data but provides KCE with a copy of the pseudony-mized database after database lock as well as a royalty-free unrestricted license to use the Study Data for non-commercial public health related purposes as detailed in the Agreement between KCE and the sponsor. If judged appropriate, KCE will introduce the request to the competent chamber of the Information Security Committee and arrange for the data linkage. For the sake of clarity, the linked data are not part of the Study Data. However, KCE will discuss with the Sponsor the results of the analyses and the reporting of the linked data.

Table 1 Overview of Study Procedures

	Screening period	Randomisa- tion	Treatment Period 			Midterm follow-up			Long-term follow-up
	Visit 1		Visit 2	Visit 3	Visit 4	Visit 5	Visit 6	Visit 7	
	Max 2 weeks af- ter dis- charge	Max 4 days after visit 1	Day of Surgery (max. 6 weeks after randomisation)	Discharge (~1-7 days after surgery)	Outpatient clinic (2-6 weeks after surgery)	6 months	12 months	24 months	5 years
Informed consent	Х								
Eligibility Assessment	X 	Х							
Randomisation		Х							
Surgical findings			X						
Registration of Physical examination and history taking 	X				X	Х	Х	Х	
Review of electronic patient data	X		X	X					Х
QoL questionnaires	Х					Х	Х	Х	
Modified iMCQ and iPCQ	Х					Х	Х	Х	
General practitioner questionnaire									Х

- 1. Visits 2-4 only apply to the intervention arm of the trial.
- 2. Screening and assessment as soon as possible after conservative treatment for ASBO.
- 3. History taking and physical examination focused on readmissions, chronic abdominal pain, and incisional hernia as described above.

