#### 4.4 Sample size calculation

Primary outcome is the time to recurrence measured at two years of prospective follow-up. We will perform a superiority trial. Based on previous literature, we expect 20% recurrence in 2-year with wait-and-see policy (based on a mix of patients with a first and recurrent episode of aSBO) and a 10% recurrence rate after intervention, resulting in a hazard ratio (HR) of approximately 0.47.

We estimated that if 378 patients were randomly assigned in a 1:1 ratio (i.e., 189 per group) to the intervention group or the control group, our study would have 80% power to detect an HR for recurrence of adhesive small bowel obstruction of approximately 0.47 at a two-sided  $\alpha$  level of 0.05. After rounding the total number of patients up, we aim to include a total of 380 patients. Analysis will be performed by intention to treat basis, using survival analysis. We will use cox regression to be able to apply multivariable analysis to account for covariates such as previous episodes of ASBO.

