Despite the existing evidence for the efficacy of adhesion barriers, they have only partly been implemented in hospitals in the Netherland and Belgium. In our group, there was

broad consensus based on the available data that adhesion barriers should be used as part of a good elective adhesiolysis. This consensus was also supported by the surgeons from the participating centres in the Netherlands and Belgium that at present do not use adhesion barriers in their daily routine. Therefore we decided to standardize their use in the trial. Barriers are provided as part of the trial to minimize the risk of difficulties with inclusion, or significant delays in local approval of a lack of availability of adhesion barriers. The use of barriers will be a focus in the implementation plan that will be made by the end of the trial.

No specific intervention or follow-up is performed in the control group of wait-and-see policy. Current standard treatment for patients with a primary aSBO is the wait-and-see policy.

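### Follow-up for the 2-year primary endpoint is described inconsistently, and up to 24 months no scheduled check would find a readmission in a patient who neither attends nor replies

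*Protocol*

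**What the plan says.** **Whether there is follow-up.** Protocol section 5.1: "No specific intervention or follow-up is performed in the control group of wait-and-see policy". Section 6.3, under Surgery: "No specific follow-up is performed after this single post-operative outpatient visit". Section 6.3, under Control arm, also excludes specific follow-up, but there the wording refers to care. Table 1 (Overview of Study Procedures, section 6.3) places history and examination at 6, 12 and 24 months (visits 5-7). Its first footnote confines only visits 2-4 to the intervention arm, so visits 5-7 apply to everyone. Section 6.1.3 says that these visits look for readmissions at other hospitals.

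**When questionnaires are sent.** Section 6.1.2 gives 1 and 2 years. Section 6.3 (Data collection), section 8.2 and Table 1 give 6, 12 and 24 months.

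**How recurrences are found.**
- Section 6.1.2 lists "Review of data from readmission in same hospital" as a sub-item of history taking at surgical follow-up. It also has patients asked about other hospitals.
- Section 6.3 (Data collection) has the questionnaires ask about missed episodes, which are then verified from medical information.
- The Table 1 row "Review of electronic patient data" is marked at visit 1, the day of surgery, discharge and 5 years.
- For long-term follow-up, after review of participating-hospital data, "short questionnaires will be sent to general practitioners to identify potential readmissions for" aSBO outside those hospitals. The protocol describes this method as accurate. Table 1 marks it at 5 years only.

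**Handling of loss.** Section 8 keeps lost patients in the survival analysis until the moment of loss.

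**The concern.** Two things are at stake. First, a site that follows sections 5.1 and 6.3 literally could omit the visits at which the primary endpoint is ascertained. Second, even if Table 1 is followed, every scheduled route up to 24 months needs something from the patient. The two sources that do not, electronic records and the GP, are timed for a secondary outcome, recurrence at 5 years.

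The protocol itself says why this matters: recurrences present at the patient's local hospital, and a patient may turn up at a hospital outside the trial group. Patients know their allocation. Whether they keep attending or replying may depend on arm and on symptoms, and censoring those who stop may then be related to their risk of recurrence. Section 6.1.1 justifies the 2-year horizon by low loss of data and by avoiding delay in using the results, so a check at 5 years may come after the primary result has been acted on.

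**Working it through.** **1. Capture routes up to 24 months, side by side**

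| Route | Where stated | Timing | Needs the patient? |
|---|---|---|---|
| Visit history, with same-hospital readmission review | 6.1.2, 6.1.3, Table 1 | 6, 12, 24 months | Yes, must attend |
| Patient questionnaire, with verification | 6.3 Data collection | 6, 12, 24 months | Yes, must reply |
| Serious adverse event report of an unplanned admission | 7.2.2, 7.3 | Continuous | No, but trial staff must become aware |
| Electronic record review | Table 1, 6.3 | After discharge, 5 years only | No |
| GP questionnaire | Table 1, 6.3 | 5 years only | No |

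The blank cells are not merely an effect of how the table was laid out. The prose on long-term follow-up in section 6.3 also places participating-hospital review and the GP questionnaire there. The uncovered group is therefore patients who neither attend nor reply, including those who withdraw.

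**2. The protocol's sample size**

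Inputs from section 4.4: "we expect 20% recurrence in 2-year with wait-and-see policy", "a 10% recurrence rate after intervention", "80% power to detect an HR for recurrence of adhesive small bowel obstruction of approximately 0.47", two-sided alpha 0.05, 378 patients rounded up to 380.

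- Hazard ratio: ln(0.90)/ln(0.80) = 0.472, as stated.
- Schoenfeld events: 4 × (1.960 + 0.842)² / (ln 0.472)² = 55.75, so 56.
- Patients: mean event risk (0.20 + 0.10)/2 = 0.15; 55.75/0.15 = 372, or 56/0.15 = 374 after rounding. This is close to the stated 378.
- At N = 380: 380 × 0.15 = 57 events; power = Φ(√57 × 0.750/2 − 1.960) = Φ(0.873) = 81%.

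The stated figure is reproduced with complete ascertainment. The slack is 6 to 8 patients in 380, about 2%, although section 6.5 says that some loss was allowed for and gives no rate.

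**3. Equal loss of events in both arms (assumed shares; the protocol gives none)**

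With share m missed, events = 57 × (1 − m) and observed hazard ratio = ln(1 − 0.10(1 − m)) / ln(1 − 0.20(1 − m)).

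| m | Events | Hazard ratio | Power |
|---|---|---|---|
| 0 | 57.0 | 0.472 | 81% |
| 5% | 54.2 | 0.474 | 79% |
| 10% | 51.3 | 0.475 | 76% |

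If the lost patients are censored non-informatively and the hazard ratio stays at 0.472, 10% loss gives Φ(√51.3 × 0.750/2 − 1.960) = Φ(0.727) = 77%, hardly different.

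**4. Unequal loss**

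The direction is open. Missing 10% of control events only gives ln(0.90)/ln(0.82) = 0.53. Missing 10% of intervention events only gives ln(0.91)/ln(0.80) = 0.42. Nothing in the protocol says which, if either, applies.

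**The case against.** The case for leaving the plan alone has substance.

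- **Capture does not depend on attendance alone.** The questionnaires reach patients who miss a visit, and reported episodes are verified. This stands. A patient who misses a visit but replies is not lost, and section 8 does not censor that patient.
- **Record review is not wholly absent before 5 years.** A reader of Table 1 might infer that it is. But same-hospital review belongs to the history taking that the table schedules at 6, 12 and 24 months, and the third footnote ties that row to readmissions. This stands, but such review comes with a visit and covers the same hospital only.
- **Unplanned admissions are reportable as serious adverse events.** This helps, but it works only once trial staff learn of the admission.
- **The statements about no follow-up may concern clinical care.** That is the likely intention, since the Control arm paragraph says so. Section 5.1 and the Surgery paragraph carry no such qualifier, so the wording still needs correcting.
- **A reader might infer that recurrences mostly present away from the operative centre.** No figure supports that. Section 6.3 allows the local hospital to be a referral or an operative centre, and referral centres can take part in the trial. Only the possibility of admission outside the participating hospitals is documented.
- **A reader might expect bias against surgery because control patients are followed less closely.** The protocol does not support this. Control patients also have a reason to report a recurrence, because it opens the option of cross-over.

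**Conclusion.** The point holds in a limited form. The protocol contradicts itself on whether follow-up takes place after the post-operative visit and in the control arm, and on when questionnaires are sent. Within 24 months no scheduled check of the primary endpoint is independent of the patient attending or replying, although the protocol has two such tools and uses them at 5 years. The resulting gap is confined to patients who neither attend nor reply, and to those who withdraw.

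How many patients that is, and whether they differ by arm, cannot be derived from the document. The loss of about 2 to 5 points of power rests on an assumed 5-10% of events missed equally in both arms. No shift in the hazard ratio should be read as predicted. This is a worthwhile and inexpensive improvement to the ascertainment of the primary endpoint; it does not show that the planned result would be biased.

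**What to change.** 1. In Table 1 of section 6.3, mark the electronic record review row at 6, 12 and 24 months in both arms, to be done whether or not the patient attends.
2. Send the existing GP questionnaire at 24 months for every patient who neither attended nor replied. Ask patients who withdraw to permit this passive check.
3. Reconcile sections 5.1, 6.1.2 and 6.3 (Surgery, Control arm, Data collection) with Table 1, so that study visits 5-7 and one questionnaire schedule clearly apply to both arms. Statements about no specific follow-up should say whether they mean clinical care or study follow-up.

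The cost is a set of table and wording changes, record review at three more time points, and a small number of GP letters sent earlier than planned. One check is needed first: the consent to contact GPs and other hospitals is worded for long-term follow-up, so confirm that it covers month 24 and amend it if it does not.
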